Participants will receive IM in the Detention Center as described above. In addition, PN will be provided for up to three months post-release. The PI, who has extensive experience with MM treatment and with MM in prison, and supervised case management as part of a recent RCT,¹⁰⁰ will be trained by PI [name] and consultant [name] (see **Letter of Support**) in [name] intervention that successfully linked heroin-dependent patients receiving medical care at San Francisco General Hospital to community MMPs.³³ The PN staff will be trained by the PI over the first two weeks of the study and will employ patient navigation which includes strengths-based management^{101,102} that will provide assessment, linkage to treatment, care coordination, patient advocacy, and monitoring. The manual used in the study by [name] (see **Appendix 1** and **2**) will be modified by the study team for Baltimore and for jail reentry.

PNers will meet with the participants assigned to the IM+PN Condition prior to their release and obtain detailed contact information from the participant. A community care plan will be developed with the inmate, including a discussion about how to select which of the four MMPs the participant wishes to attend upon release. The PNers will coordinate this decision with nursing, so that the nurses may make arrangements to transfer the participant's records to the receiving program. Because detainee releases can occur at any time of the day, the PNers will provide the participants with their cell phone and office numbers and encourage participants to call them upon release. The PNers will also routinely check the roster of the detention center to identify any individuals who have been released and will reach out to ensure contact with newly-released inmates through the detailed contact information collected at baseline.

PN services will be focused on facilitating entry into community-based drug abuse treatment and addressing barriers to re-entry and retention in treatment. These barriers may include difficulty obtaining appointments at community-based MMPs, challenges interacting with clinic staff, transportation (obtaining bus

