passes), housing challenges, and fluctuating motivation. Gender-specific issues will be addressed, such as obtaining child care and referrals to treatment for drug using significant others. PNers will arrange to meet the participant at the selected MMP for the first visit to maximize the likelihood of keeping the appointment. PNers will remain with the participant during the intake process to assist in communication with the MMP if necessary and to advocate for the participant. They will also facilitate keeping treatment appointments through reminders, coaching, and if necessary, meeting the participant either at the MMP or in the community to accompany them. The PNers will call participants who miss appointments to determine what happened and to facilitate another appointment or referral. PNers will seek out participants if they cannot be reached by phone (much the same way that our research staff now does for follow-up interviews using extensive locator information).

Once a participant is enrolled in treatment, the PNer will assist them (if necessary) in gaining an ID card and will provide them with bus or train tokens for the first few weeks until a reduced fare bus pass can be obtained. If necessary, navigators will assist the participant in complying with the instructions provided by the clinic staff in completing required documentation to obtain Medicaid or Maryland's state health benefits that will pay the clinic for treatment, whether MM or some other modality. Limited funds will be available for the PNers to obtain bus tokens, and to pay for ID cards and other needed low-cost services.

It is anticipated that the PNers will meet with the participants weekly during the first month, and about every other week (or more) during the second and third months, as needed. Phone calls will be made in between appointments or used as reminders or to seek the participant out if appointments are missed.¹⁰³ As needed, the PNers will go into the community to find the participant at their home or usual hangouts to try to reengage them following the procedures that we use successfully in tracking this population for research follow-ups. The PNers will enter in an excel database and written progress notes all of their participant-related activities including all attempts at contacting participants, PN services delivered, site of PN services, referrals made, and community services received.

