Arrest and incarceration (Criminal Justice Records)	◆	12-months only

* Participants transitioning directly to other community MMPs or buprenorphine treatment will be considered still in treatment.

† Consistent with prior research, the SASCAP will be administered once during the treatment phase.

Participants will be paid \$30 for follow-up interviews (regardless of whether they are conducted in the community or during a re-incarceration) and will provide consent for research staff to check hospital and arrest records. Participants who are interviewed for follow-up during a re-incarceration will have the option to receive their \$30 deposited into their jail or prison account or to have a money order mailed to a designated person. They will not be paid for the baseline interview conducted in jail to avoid the perception of coercion.

Longer-term follow-ups: Participants will be asked (using a consent form addendum) if they'd be willing to have a 24-month follow-up interview for which they would be paid \$40. The 24-month interviews will include the same assessments as the 12-month interviews described above. In addition they will be asked if the research team could contact them beyond the 24-month follow-up for further informed consent for even longer-term follow-up interviews.

Measures for Aim 1 and 2:

Entry into Treatment: within the first 30 days of release from jail will be obtained from patient self-report from the Methadone Treatment Exposure form.

Enrollment in Treatment: will also be obtained from self-report on the Methadone Treatment Exposure form.

Addiction Severity Index (ASI): assesses patient functioning through a 30-45 minute interview covering 7 key domains over the past 30 days including drug and alcohol use, legal, medical, psychiatric and employment status, family functioning and social relations.¹⁰⁶ Composite scores and items from each domain will be investigated (with particular emphasis on drug use and legal scores and items).

Urine Drug Testing: Urine samples will be collected by project staff at 1, 3, 6, and 12 months post-baseline and tested by an approved rapid drug test cup for opiates, methadone, buprenorphine, cocaine, and benzodiazepines. Results will be used for research purposes only and will not be shared with clinic staff.

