Methadone Dose: Higher methadone maintenance doses in jail have been shown to be related to higher rates of treatment entry following release from incarceration²² and improved retention rates in community-based treatment.⁴⁶ As such, methadone dose will be recorded at release from the Detention Center and at each follow-up to permit an examination of the relationship between methadone dose and outcomes by treatment Conditions.

Overdose AE Form. This brief 12 item questionnaire was devised for the present study to examine the number and characteristics and responses to any non-lethal overdoses between study visits.

Methadone Treatment Exposure Questionnaire. This brief 7 item questionnaire was devised for the present study to examine methadone treatment status, anticipated length of sojourn in methadone treatment, and reasons for leaving treatment (if applicable).

Measures for Aim 3:

Economic Form 90: The Economic Form 90 survey has been modified for our ongoing research in MMPs and used successfully to collect data on participant outcomes and economic outcomes before, during, and after treatment. This instrument is useful to supplement the ASI whose time frame for follow-up interviews is restricted to the past 30 days for items such as arrest and hospitalization. The Economic Form 90 is a modified version of the Form 90 family of instruments that was originally designed to collect alcohol use and economic outcome data for alcohol treatment studies.^{112,113} It will be used to collect data on residential drug treatment, outpatient, and emergency room health care utilization; criminal behavior including number of arrests, severity of offense, and nights incarcerated. Also collected will be labor market information including employment status, current wage, frequency of work, and amount of money received beyond paid employment (e.g., Social Security) and off-the-books earnings.

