The Principal Investigator is responsible for informing NIDA of any safety-relevant actions taken by WIRB as a result of its regular annual reviews and any special reviews of this project. In addition, the PI will inform NIDA of any major changes in the protocol or its status including: protocol amendments; procedural changes; suspension or termination of subject accrual or of the protocol itself; changes in the informed consent or IRB approval status; and other problems or issues that could have a significant impact on individuals' consent to participants. The PI will provide the minutes of the DSMB meetings to NIDA.

Serious Adverse Event Reporting

Serious adverse events (SAE's) include any of the following outcomes for the participant: 1) death; 2) acute life-threatening incidents; 3) hospitalization or the prolongation of a hospitalization; 4) persistent or significant disability or incapacity; or, 5) birth defects. Should they occur, these events may be communicated to the PI by participants and/or staff, or may be observed directly by the PI. SAE's will be reported to the UCLA DSMB and NIDA regardless of whether they are considered study related.

In any given case, the PI will make an initial SAE report to the DSMB and the study's medical safety monitor within 48 hours. SAEs that are unexpected and definitely or probably study related will also be reported to the DSMB within 48 hours. The PI will submit follow-up reports on participants who have experienced an SAE until the outcome of the event is known. This follow-up information will be reported to the DSMB and NIDA staff. A summary of SAEs will be reported to NIDA Program staff through the annual non-competing renewal application mechanism.

Reporting of Unanticipated Risks or New Findings

The PI will report any information related to unanticipated risks or new information that may change the risk-benefit ratio to WIRB and DSMB, and the NIDA Program Official. This information may consist of findings from the current study or other studies. Any changes in the protocol or informed consent as a result of this information will be promptly reported to the NIDA Program Official.

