As in all of FRIs randomized clinical trials including our studies of interim methadone and methadone treatment in prison, a DSMB of outside experts in clinical trials and biostatistics will be created to review the progress of the study and monitor participant intake, outcomes, SAEs, and other safety related matters. The DSMB will meet at the start of study enrollment and every six months for the first year of enrollment and annually thereafter. Members will include a physician expert in the opioid agonist maintenance treatment of heroin dependence and a statistician. The DSMB will review all SAEs. The project's statistician will perform interim analyses, if so requested by the DSMB, to determine whether the study should be terminated early as a result of preliminary findings. The Board will also review study enrollment and feasibility as well as the nature and frequency of SAEs in reviewing the safety of the study. DSMB meetings will be convened as needed to discuss new findings, unexpected SAEs that are considered related (or probably related) to the interventions under study, or results of any other new findings in the literature that pertain to this study. All DSMB reports will be sent to the PI who will forward copies to the IRB and to NIDA.

Criteria for Suspending or Terminating the Study

The study may be modified, suspended, or terminated at the recommendation of the PI, DSMB, or by WIRB in the interests of protecting study participants. The study will be modified to comply with any FDA-approved labeling changes for methadone administration. The PI, DSMB, or IRB may recommend modifying, suspending, or terminating the study based on the SAE reports. Trials may be terminated for any one or more of four classes of reasons as determined by the DSMB, as specified below: 1) safety/adverse events; 2) favorable benefit-risk ratio; 3) unfavorable benefit-risk ratio; and 4) inability to answer questions regarding trial efficacy.

Termination Due to Safety/Adverse Events:

The DSMB's recommendation to stop the study with regard to safety/adverse event considerations will be based on the number and severity of unexpected, study-related SAEs.

Termination Due to Favorable Benefit-Risk Ratio:

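### SAE ascertainment is not standardized across arms, and for up to three months after release only IM+PN has frequent navigator contact, so by-arm SAE counts are open to detection bias

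*Combined protocol and SAP*

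**What the plan says.** Under Serious Adverse Event Reporting, SAEs "include any of the following outcomes for the participant: 1) death; 2) acute life-threatening incidents; 3) hospitalization" or its prolongation, disability and birth defects. On how they come to light, the section says only: "these events may be communicated to the PI by participants and/or staff, or may be observed directly by the PI". Figure 1 schedules no SAE form. The Overdose AE Form, given at 1, 3, 6 and 12 months, is meant "to examine the number and characteristics and responses to any non-lethal overdoses between study visits".

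Section 6.c gives navigators to one arm only. It anticipates that "PNers will meet with the participants weekly during the first month, and about every other week (or more) during the second and third months". The frequency is to follow need, with phone calls in between and outreach to participants' homes when appointments are missed. The duration is limited: "PN will be provided for up to three months post-release". Navigators log all their participant contacts. The investigator, who also makes the SAE reports, meets them weekly and reviews those logs and notes.

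Research interviews (Section 7) follow the same schedule in all arms. The text after Figure 1 adds that participants "will provide consent for research staff to check hospital and arrest records". The DSMB section states: "The DSMB will review all SAEs". It also says that the board considers how often SAEs occur and of what kind.

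**The concern.** An event that becomes known only if someone mentions it is more likely to become known where contact is more frequent. Here the extra contact is part of the randomized intervention, so it differs by arm by design. It also feeds into a weekly meeting with the person who reports SAEs. IM alone and ETAU have no matching channel.

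The imbalance falls in the early post-release period, which the protocol's own background treats as the time of rapid relapse and raised overdose-death risk. With equal true risk, IM+PN could show more recorded SAEs. Neither the DSMB nor a later reader could tell whether the excess came from the intervention or from closer observation.

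**Working it through.** The plan states no SAE rate, capture probability or safety sample size, so there is no figure to reproduce. Two checks are possible.

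**1. Planned study contacts in the first three months after release**

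- Month 1, weekly: 52/12 = 4.3 meetings.
- Months 2 and 3, every other week: (2 × 52/12)/2 = 4.3 meetings.
- Navigator total: 8.7, that is, about 8 to 9 meetings (Section 6.c).
- Research interviews at months 1 and 3: 2 in every arm (Section 7).
- Result: about 10 to 11 contacts in IM+PN against 2 in IM alone and 2 in ETAU.
- Months 3 to 12: 2 interviews in each arm, so planned contact is equal.

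This takes Section 7's post-release timing; the Abstract and Project Timeline say post-baseline. The count leaves out navigator phone calls and outreach, and also community clinic contact for IM participants who enter treatment. Contacts are not detection rates, so the count shows the asymmetry but not its effect.

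**2. What unequal capture would do (all inputs assumed except the arm size)**

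Inputs: 100 per arm (Project Timeline); true risk p of an SAE in the navigation window, equal in both arms; capture 95% in IM+PN and c in the comparison arm. Recorded risk = p × capture, so the spurious ratio is 0.95/c, whatever the value of p. The last two columns give the chance that a two-sided Fisher's exact test reaches p < 0.05. The test serves only as a yardstick, since the plan has no such test.

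| c | Recorded risk at p = 10% | Spurious ratio | Chance of p < 0.05 at p = 10% | Same, for p from 5% to 20% |
|---|---|---|---|---|
| 95% | 9.5% v 9.5% | 1.00 | 2.8% | 2.0% to 3.3% |
| 90% | 9.5% v 9.0% | 1.06 | 2.9% | 2.0% to 3.6% |
| 70% | 9.5% v 7.0% | 1.36 | 6.0% | 2.8% to 11.9% |
| 50% | 9.5% v 5.0% | 1.90 | 15.9% | 5.6% to 37.4% |

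These ratios apply to the navigation window. Over 12 months they are diluted. If a share s of SAEs falls in the window and capture afterwards is c in every arm, the 12-month ratio is 1 + s × (0.95/c − 1). With events spread evenly, s = 3/12 = 0.25:

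- c = 90%: 1 + 0.25 × 0.056 = 1.01
- c = 70%: 1 + 0.25 × 0.357 = 1.09
- c = 50%: 1 + 0.25 × 0.90 = 1.23

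Early clustering of events would push these back towards the window figures.

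**Deaths.** Expected follow-up is about 90%, so roughly 100 × 0.10 = 10 participants per arm may not be interviewed. No systematic source for their vital status is named, although navigators would be actively seeking out IM+PN participants early on.

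**The case against.** Much is already symmetric. The ASI is given at 1, 3, 6 and 12 months in all arms. It has a medical domain, and the Economic Form 90 description shows that its 30-day items include hospitalization. Economic Form 90 covers health-care use at 3, 6 and 12 months. The 1-month ASI spans nearly all of the first month at risk. The SAE section is permissive, not exclusive, and staff includes the interviewers who see every arm. Navigator meetings are anticipated and as needed, and last at most 3 of 12 months. No between-arm SAE test is planned. The safety stopping recommendation rests on unexpected, study-related SAEs, while substance-use harms and known methadone side effects are classed as expected.

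All of this stands, and it rules out several stronger readings that a reader might infer:

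- *Harm rates in general cannot be compared.* Non-lethal overdose and health-care use are collected with the same instruments on the same schedule in each arm.
- *The overdose form is defective because it omits deaths.* No participant questionnaire can record that participant's death, and death is the first SAE category. Overdose is not among the Aim 1 and 2 outcomes. The supportable point is that the form should not be read alone as an overdose comparison between arms.
- *IM+PN will show an excess.* With 95% v 90% capture there is almost none.
- *The safety stopping criterion would be driven by the bias.* It uses a narrower set of events than all SAEs.

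The objection does not close one gap: nothing in the plan turns an interview answer into an SAE report, in any arm. Neither the 30-day ASI items nor a health-care form absent at month 1 is tied to SAE reporting.

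**Conclusion.** The concern holds for SAE counts: hospitalization, life-threatening events, disability and death. Their ascertainment is not standardized, and for up to three months one arm has an additional channel to the person who reports them. Any by-arm SAE count shown to the DSMB or published later is open to detection bias, with IM+PN the arm likely to look worse. The documents do not say whether DSMB tables are split by arm, so the consequence depends on such a split being made there or in later reporting.

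The size cannot be determined. The range of 1.06 to 1.90 for the window rests wholly on assumed capture rates and equal true risk, and shrinks to about 1.01 to 1.23 over 12 months if events are spread evenly. No efficacy analysis is touched. This is a cheap improvement, not a flaw that threatens the trial's conclusions.

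**What to change.** 1. At the existing 1-, 3-, 6- and 12-month interviews, ask the same short SAE questions in all three arms, covering the whole period since the last visit.
2. State that hospitalization and health-care answers on the ASI and Economic Form 90 trigger SAE follow-up in every arm.
3. Determine vital status for every participant in each visit window, using the locator and tracking procedures already described under Follow-up and Attrition.
4. Base by-arm SAE tables on that common source. Keep navigator and other spontaneous reports for expedited reporting, and flag each SAE by source.
5. Present overdose per participant as fatal plus non-fatal.
6. Use hospital records only after reconciling two places. The text after Figure 1 says participants consent to hospital-record checks. The consent content under Participant Recruitment (Human Subjects) lists treatment, arrest and incarceration records but not hospital records.

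Cost: a few interview minutes per visit and one extra column in the DSMB table. No treatment procedure changes.

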They will be informed that if they are assigned to the interim methadone + patient navigator condition, a study staff member serving as patient navigator will meet with them in the detention center to assess potential barriers to their entry into methadone treatment upon release. They will be told that the navigator will be available to them for three months after release to help them enter and remain in treatment. These services may include help: getting a bus pass, arranging childcare, and referring their significant others to drug abuse treatment. Navigators will also be available to provide advocacy for them with their drug treatment program.

Participants will be informed that they will receive a series of assessments at study entry and at 1, 3, 6, and 12 months post-release. A urine sample will be collected during the assessments in the community. They will be told that all of their urine test data and responses to the assessment questions will be confidential and will not effect their treatment at the detention center or in the community. The limits of confidentiality will be explained including threats of harm to self or others, child or elder abuse, or certain communicable diseases (e.g., tuberculosis). They will be informed that their study involvement requires their consent for the research staff to obtain their methadone treatment data from his/her detention center methadone program record, treatment information from the methadone program in the community that they attend as well as admission, discharge dates from any other public drug treatment programs attended during the course of the study, and their arrest and incarceration records from the criminal justice system.

In addition, participants who provide a signed informed consent addendum will be interviewed at 24-months after enrollment using the same interview and urine collection approach as for the 12-month interview.

Potential risks

Risks of substance abuse. Risks of opioid and/or other substance abuse include: overdose death, infections including but not limited to endocarditis, soft tissue infection, hepatitis, kidney infection, HIV infection, seizure, stroke, and trauma from motor vehicle, machinery, or violence.

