Risks of methadone treatment. The use of methadone in this study poses no additional risk than that of methadone provided under routine treatment conditions in the methadone clinics in the detention center and in the community. When taken under medical supervision, methadone is a generally safe and effective treatment for opioid detoxification and maintenance. The major risk of methadone treatment (as with heroin and other opioids) is over-sedation which can lead to respiratory depression and death from overdose. This can very rarely occur during the initial phase to methadone dose induction. Participants assigned to detoxification will be treated with low doses of methadone and will be carefully monitored by nursing staff on a daily basis making this risk very unlikely. Participants in interim methadone treatment will begin treatment with a low dose which will be slowly increased. They too will be monitored by nursing on a daily basis, making this risk unlikely as well. Interim methadone treatment has been found to be as effective as methadone with counseling early in the first four months of methadone treatment in community-based settings where there is even more opportunity to use illicit drugs than during incarceration. Therefore, interim methadone should not

pose any additional risks than standard methadone treatment. All participants will be informed of the availability to all detainees of mental health counseling for depression and suicidal ideation while incarcerated should they need it.

Potential participants will be told that the most often reported side effects of methadone (some of which are associated with receiving too low or too high a dose) are trouble sleeping, nervousness, drowsiness, dizziness, vomiting, sweating and constipation. Operating an automobile or machinery may pose risk if the participant becomes drowsy. Other side effects may include palpitations and fainting which could be a sign of an irregular heart beat, which could in very rare instances lead to sudden death. Other individuals may experience trouble urinating, decreased sexual desire or potency, or allergies (including itching, rashes and swelling). Stopping methadone treatment suddenly will lead to opiate withdrawal symptoms. Finally, if the participant becomes pregnant during methadone treatment, they should seek obstetrical care.

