Emotional discomfort. There is a small chance that participants may become upset when discussing their history of drug use or sexual behavior or responding to any of the self-report measures or interview questionnaires. We will discontinue administration of research instruments if a participant shows discomfort. If necessary, the PI or Co-I [name], both psychiatrists, or medical staff from the Detention Center will meet with the participant to alleviate any problems.

Confidentiality. Participants will be asked to provide information regarding a number of sensitive behaviors (e.g., drug use, sexual behaviors, and illicit activities). The inappropriate release of such confidential information could result in loss of employment, arrest, or social problems. Careful steps to minimize such risks will be taken as described below.

Protection Against Risks

Risks Associated with Substance Abuse. The above-mentioned risks of continued substance use are considered symptoms of the participants' underlying substance use disorder and serious adverse events related to these risks are to be considered expected. Efforts to minimize these risks include providing at a minimum enhanced treatment as usual (ETAU) in all three study conditions which includes providing drug abuse information, overdose prevention information, and a referral to community harm minimization (needle exchange and overdose prevention) as well drug abuse treatment programs.

Risks Associated with Methadone Treatment. Every effort will be taken to minimize the likelihood of risks to participants that are associated with the known side effects of methadone as described in its FDA-approved label. Any known side effects of methadone treatment will be considered expected adverse events.

In an attempt to reduce potential risks associated with methadone treatment, participants receiving methadone (detoxification or interim) treatment will be carefully monitored by trained nursing and medical staff who are working in accredited methadone treatment program. Methadone program staff provide patient education on methadone and its side effects. A slow dose induction process, including daily observation by nursing will minimize the likelihood of oversedation and overdose death during the dose induction process. Methadone treatment in the community will be standard care and its risks will not differ from those routinely offered to patients in the US.

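### The DSMB's specific criterion for a safety stop leaves out overdose deaths in every arm, because the protocol has already classed them as expected

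*Combined protocol and SAP*

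**What the plan says.** Four parts of the combined protocol and SAP bear on this.

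- **Potential risks.** Under substance abuse: "Risks of opioid and/or other substance abuse include: overdose death", followed by other harms. Under methadone treatment, the major risk "is over-sedation which can lead to respiratory depression and death from overdose".
- **Protection Against Risks.** For the substance-abuse risks listed earlier, "serious adverse events related to these risks are to be considered expected". For methadone, "Any known side effects of methadone treatment will be considered expected adverse events".
- **Data and Safety Monitoring Plan: reporting and review.** Every SAE, related or not, goes to the DSMB and NIDA. The initial report to the DSMB and the medical safety monitor is due within 48 hours. The DSMB reviews all SAEs, including their nature and frequency. Unscheduled meetings may be called for new findings, for "unexpected SAEs that are considered related (or probably related) to the interventions under study", or for relevant new literature.
- **Criteria for Suspending or Terminating the Study.** A general sentence says the PI, DSMB or IRB "may recommend modifying, suspending, or terminating the study based on the SAE reports". Four classes of reasons for termination then follow. The safety class is defined in one sentence: the DSMB's recommendation "will be based on the number and severity of unexpected, study-related SAEs".

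**The concern.** A stopping criterion limited to unexpected events works when the worst foreseeable outcome is not on the expected list. Here it is on the list. The Abstract and the section on post-release relapse both present overdose death after release as a central hazard. The consent content under Participant Recruitment tells ETAU participants, and interim methadone participants who stop, that they may face a greater chance of overdose if they resume use. A difference between arms is therefore foreseeable.

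An excess of an expected event is recognised by comparing its frequency between arms. The specific criterion asks instead whether each event was unexpected and study-related. A board following that sentence would set overdose deaths aside. A board following the general sentence before it would not. The participants are prisoners, and the plan should not leave that choice open for the most foreseeable cause of death.

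**Working it through.** The plan states no numeric safety boundary, so there is no figure to reproduce. The check traces the definitions.

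1. **Overdose from substance use.** Potential risks names overdose death among the harms of substance abuse. Protection Against Risks refers back to those harms and makes SAEs related to them expected. Such a death is therefore an expected SAE.
2. **Overdose from methadone.** Potential risks names fatal over-sedation as methadone's major risk. Protection Against Risks makes known side effects expected. Treating the named major risk as a known side effect is a small inference, but the natural one. On that reading this death is also expected.
3. **The specific criterion.** It requires an SAE to be both unexpected and study-related. Steps 1 and 2 fail the first condition, so the event is not counted.
4. **The second condition.** Protection Against Risks describes the overdose risk after detoxification, or after stopping methadone, as no different from the risk outside the study. That points towards a judgement of not study-related, so many of these deaths would probably fail the second condition too.
5. **Result.** Overdose deaths counted = 0 in IM+PN, 0 in IM alone and 0 in ETAU, at any true frequency.

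An illustration with assumed counts, using the planned 100 participants per arm (100 ETAU against 200 on interim methadone) and Fisher's exact test, two-sided:

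- 3 deaths v 0: p = C(100,3)/C(300,3) = 161,700/4,455,100 = 0.036.
- 4 deaths v 1: p = 0.044.

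Both patterns would enter the specific criterion as zero. They are not forecasts.

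Next, whether another provision restores what the sentence leaves out:

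| Provision | Expected events covered? | Sets a standard for stopping? |
|---|---|---|
| General authority to act on the SAE reports | Yes | No; permissive only |
| DSMB review of all SAEs | Yes | No |
| 48-hour SAE report to DSMB and medical monitor | Yes | No |
| Unscheduled meeting for SAEs | No; unexpected and related only | Calls a meeting |
| Unscheduled meeting for new findings | Could be read to include them | Calls a meeting |
| Stop for unfavorable benefit-risk | Safety is a further consideration | Starts from interim efficacy results |
| Stop for safety | No | Yes; this is the stated criterion |

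Information flow and general authority both cover overdose. Among the provisions that define a ground for stopping, the safety one does not.

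**The case against.** The strongest reply is that the DSMB can already act. The general sentence has no expectedness or relatedness limit, and termination is also allowed in order to protect participants. Every SAE arrives within 48 hours, meetings can be called for new findings, and new or increased risk is promptly reportable to WIRB. The board includes a statistician and may request interim analyses, so nothing prevents a by-arm table. All of this stands, and it confines the point to one criterion in conflict with wider authority.

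It does not remove the conflict. The general sentence permits action without saying what should prompt it. The text then says the classes of reasons are specified below, and specifies the safety class in terms that exclude overdose. No section requires SAEs to be compared by arm.

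Two stronger readings are tempting, and the documents support neither.

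- **That the trial has no means of stopping for overdose deaths.** The general authority and the reporting rules contradict this.
- **That participants enrolled late are unmonitored.** The DSMB meets at the start and then "every six months for the first year of enrollment and annually thereafter". With recruitment of about 22 months, the last scheduled meeting during enrollment is at month 12, after which about 300 × 10/22 = 136 participants would enter at an even pace. But each SAE is still reported within 48 hours and meetings can be called between scheduled dates. Meeting frequency is a separate preference.

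**Conclusion.** The point holds for the sentence that defines a safety stop. Under the protocol's own classification, overdose deaths cannot count towards it in any arm. That conflicts with the broader authority in the same section, and the omitted event is the main foreseeable harm.

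The size is definitional: zero countable overdose deaths under that sentence. It is not an estimate of missed harm, since the documents give no overdose rate and the DSMB can act by other routes. The conclusion assumes that the sentence is read as written and, for deaths from methadone alone, that the named major risk counts as a known side effect. For overdoses related to substance use, the second assumption is not needed.

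**What to change.** Replace the sentence under Termination Due to Safety/Adverse Events with wording such as:

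*The DSMB will judge safety from the number and severity of SAEs, reviewed by study arm. Deaths and overdoses count whether or not they are expected or judged study-related.*

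In Protection Against Risks, keep the expected label and state that it governs reporting only.

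The cost is a short amendment with the required approvals (the protocol names WIRB, the state corrections research committee and OHRP) and a by-arm table built from SAE reports already collected. No new data are needed.

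I would not add a numeric trigger. Take one that calls a meeting when one arm leads each other arm by three overdose deaths at any time. With 100 per arm and assumed risks, simulation has it firing in about 36 to 37% of trials at 3% v 1% v 1%, and in about 37 to 38% when all arms are at 3%. It cannot tell those situations apart, and it handles harm shared by both interim methadone arms poorly. Neither an extra scheduled meeting nor a change to the consent wording is needed to resolve the conflict.
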